16.8 Protocol Deviations

All participant-level deviations from protocol procedures, evaluations, and/or visits must be documented. When possible, missed visits and procedures must be rescheduled and

MTBVAC	2		
Biofabri	protocol	number:	202

15	Apr 202	1 Fina	I Version	40

performed at the nearest possible time point to the original schedule. Deviations will be reported to the IRB/IEC and applicable national regulatory authorities per their guidelines.

17 PUBLICATION POLICY

The final study report will be made available to the principal investigator for purposes of publications. The principal investigator and study staff must send all manuscripts, abstracts, and presentations using data from this study to Biofabri for review prior to their submission. Biofabri jointly and separately reserve the right to delete any part or parts of such materials deemed to be confidential or proprietary.

The International Committee of Medical Journal Editors (ICMJE) member journals have adopted a trials-registration policy as a condition for publication. This policy requires that all clinical trials be registered in a public trials registry such as ClinicalTrials.gov, which is sponsored by the National Library of Medicine. It is the responsibility of the sponsor to register this trial in an acceptable registry prior to the start of participant enrollment.

The ICMJE defines a clinical trial as any research project that prospectively assigns human subjects to intervention or comparison groups to study the cause-and-effect relationship between a medical intervention and a health outcome. Studies designed for other purposes, such as to study pharmacokinetics or major toxicity (e.g., Phase 1 trials), would be exempt from this policy.

18 CHANGES TO THE PROTOCOL

Changes between protocol versions are described below.

18.1 Changes from Version 3.0 to Version 4.0

Section Number (Title)	Change/Rationale
Title page	Protocol version and date updated.
Section 2 Key Roles	TCD address updated (Drive vs Road).
Section 3.2 Rationale	Grammar update. Rationale updated to include explanation for additional safety and immunogenicity analysis/review which will determine the optimal dose level for the Phase III study. Saving time to start Phase III will be a major public health benefit as indicated in the text. Included confirmation of when the clinical team would be unblinded, for clarity.
Section 6.3.2 Masking Procedures	Included confirmation of when the clinical team would be unblinded for clarity. Grammar update. Inclusion of "D" to confirm the Study D365, visit instead of just 365 visit, to clarify.
Section 8.3 Follow-up	Updated naming of study visit to avoid ambiguity and for clarity of the addition of 7 (days).

Section Number (Title)	Change/Rationale								
Section 8.3 Follow-up (Study Day 182)	Unblinding of data for safety and immunogenicity to independent biostatistician in order to determine most optimal dose for Phase III study without compromising data integrity. Confirmation that the immune response to MTBVAC at D182 is predictive of the memory response at D365 is included below:								
	The original study was designed to analyse the antigen-specific CD4 T cell response induced by escalating doses of MTBVAC at timepoints defined to represent an acceptable assessment of the immune response kinetics (at days 28, 56, 182 and 365 post vaccination). Based on previous studies (Soares et al, JID, 2013, [name] et al, Lancet Resp. Med., 2019) vaccine-induced T-cell immune responses are expected to peak between 7 and 10 weeks post-vaccination (D28 and D56 in our trial), then to gradually wane over the subsequent 10 months of follow up.								
	In the context of an interim analysis necessary for the vaccine dose selection to inform the MTBVAC phase 3 trial, we determined if assessment of immune responses at D182 post-MTBVAC vaccination is predictive of memory responses at D365. We reanalysed immunogenicity data from the phase IIa trial ([name] et al, Lancet Resp. Med., 2019), and assessed the strength of correlation between MTBVAC-specific total CD4 T cell responses (IFN-g, IL-2, TNF, IL-17 and/or IL-22) at D180 and D360 following MTBVAC vaccination (Figure 1). At the vaccine dose analysed (2.5 x 10³ CFU, 2,5 x 10⁴ CFU and 2.5 x 10⁵ CFU), the MTBVAC-specific CD4 T cell responses between D180 and D360 were strongly correlated, suggesting that D182 is predictive of vaccine induced memory response at 1 year post-vaccination.								
	In addition, we will also determine if the cytokine co-expression patterns indicate evidence of excessive T cell differentiation, which can lead to poor long-term memory responses.								
	MTBVAC all doses MTBVAC 2.5 x 10 ³ MTBVAC 2.5 x 10 ⁴ MTBVAC 2.5 x 10 ⁵ MTBVAC 2.5 x 10 ⁴ MTBVAC 2.5 x 10 ⁵ MTBVAC 3.5 x 10 ⁵ MTBVAC 4.5 x 10 ⁵ MTBVAC 4								
Section 8.4 Follow-up (Final Study Visit)	Included confirmation of when the clinical team would be unblinded for clarity. Updated grammar.								

Section	Change/Batianala
Number	Change/Rationale
(Title)	
Section 10.7	Included when DSMB to review overall available safety data to confirm if any safety issues
Safety	for any cohort doses. DSMB to confirm safest dose for Phase III study.
Oversight	
(DSMB)	LILL BOND
Section	Included when DSMB to review overall available safety data to confirm if any safety issues
12.3.1 Planned	for any cohort doses. DSMB to confirm safest dose for Phase III study.
Interim	
Analyses –	
Safety	
Review	
Section	Included when DSMB to review overall immunogenicity data up to D182 for all cohorts to
12.3.2	confirm which dose is most immunogenic and whether MTBVAC is superior to BCG
Planned	immunogenically. This will assist in dose selection for the Phase III study.
Interim	
Analyses -	
Immunogeni	
city or	
Efficacy	
Review Section	Clarification of supporting document involved.
12.4.3	Clarification of Supporting document involved.
Immunogeni	
city and	
Other	
Immunology	
Analyses	
(Final	
Analysis)	
Section 16.4	Grammar update.
Data	Inclusion of injection site reactions previously not included in previous versions of the protocol.
Capture Methods	
Section 16.5	To collate information mentioned in previous sections. Included when DSMB to review
Timing/Rep	overall immunogenicity data up to D182 and all available safety data for all cohorts to
orts	confirm which dose is most safe and immunogenic. This will assist in dose selection for
	Phase III.
Section 16.6	Inclusion of injection site reactions previously not included in previous versions of the
Types of	protocol.
Data	
Header	Protocol version and date updated.

APPENDIX A. SCHEDULE OF EVENTS

		Study day Visit Window (hrs/days)							
Evaluation	Screen	D0	D7	D28	D56	D182	D365	Post D365	Early termination
	NA	+96 hrs	±3d	±3d	±7d	±14d	±14d	NA	NA
Informed consent process	Ma								
Medical history	М								
TB symptoms or household TB contact	М	х	Х	х	х	х	х	х	х
Maternal HIV result available	М								
Verbally reconfirm consent	М	М	М	М	М	M	М	М	
Verify eligibility criteria	Х	Х							
Vital signs, length, weight		Х	Х	х	х	х	Х	Х	X
Record feeding practice		Х	Х	Х	Х	х	х	х	х
Physical examination		Х	Х	Х	Х	х	х	х	х
Recording of concomitant medication		Х	Х	х	Х	х	х	х	х
Randomization		Х							
MTBVAC/BCG administration		Х							
Safety blood sampling (mL) ^b			2						
QuantiFERON®-TB Gold Plus (mL)b					4 ^d	4	4		4
Whole blood (mL) ^b				2	2	4	4		
(12-hour WB-ICS)							7		
Distribute/review diary cards		Х	Х						
Solicited systemic adverse events (incl. concomitant medications)		х	x	х					
Unsolicited adverse events (incl. concomitant medications)		х	x	х	х	х	х		х
Solicited and unsolicited injection site reaction adverse events (incl. concomitant medications)		х	х	х	х				
Serious adverse events (incl. concomitant medications)		х	х	х	х	х	x		x
Site of injection examination swab if discharge		х	Х	х	х	х	х		x
Rescue dose BCG post unblinding of cohort ^c								x	
Approximate per visit phlebotomy volume (mL) ^a			2	2	6	8	8		4
Cumulative phlebotomy volume (mL)b			2	4	10	18	26		NA

^a Maternal - the mother signs once, antenatally, and thereafter reconfirms consent orally at each visit

^b Acceptable infant blood sample volumes in clinical research are limited to <3% of the total blood volume (TBV), and no more than 3mL/kg over an 8 week period

^c Telephonic contact/ home visit approximately 14 days post BCG to confirm infant's wellbeing incl. BCG injection site reaction

^d If QFT positive at D56 a home/telephonic visit will be done at D120±7d and 270±7d to monitor infant's wellbeing, specifically enquiring about TB signs and symptoms

APPENDIX B. TABLE OF TOXICITY REFERENCE RANGES FOR GRADING OF ADVERSE EVENTS

Local Site of Injection Symptoms	Grade 1	Grade 2	Grade 3	Grade 4
Tenderness (pain when area is touched)	Minimal or no limitation of use of limb	Limitation of use of limb OR greater than minimal interference with usual activities	Inability to perform usual activities	N/A
Erythema (Redness)*	>2 - ≤20 mm maximum diameter	>20 - ≤50 mm maximum diameter	>50 mm maximum	Local or extensive exfoliative dermatitis
Induration *	>2 - ≤20 mm maximum diameter	>20 - ≤50 mm maximum diameter	>50 mm maximum	Local or extensive exfoliative dermatitis
Ulceration *	>2- ≤15 mm maximum diameter	>15- ≤30 mm maximum diameter	>30 mm maximum diameter	Requires hospitalization or non-routine treatment
Scar at Injection Site*	>2- ≤15 mm maximum diameter	>15- ≤30 mm maximum diameter	>30 mm maximum diameter	Keloid or extensive scarring
Regional lymphadenopathy	Non-tender, isolated, <3cm, mobile, non- fluctuating	Tender, multiple matted nodes, fixated, non- fluctuating	Supparative lymphadenitis	Supparative lymphadenitis with fistula formation
	ord maximum diameter in mm			
General symptoms	Grade 1	Grade 2	Grade 3	Grade 4
Decreased oral intake	Minimal decrease in oral intake	Below 50% of normal oral intake in 24 hr	No oral intake in 24hr	N/A
Vomiting	1 episode in 24hr; no interference with activity	2-3 episodes in 24 hr OR some interference with activity	> 3 episodes in 24 hours OR prevents daily activity	N/A
Diarrhea	Unformed stool OR 1-3 more stools than baseline in 24 hr	Partially liquid stools OR 4-6 more stools than baseline in 24hr	Completely liquid stools OR >6 more stools than baseline in 24 hr	N/A
Irritability	Easily consolable; minimal or no interference with activity	Difficult to console; some interference with activity	Inconsolable; prevents daily activity	N/A
Lethargy	Minimal decrease in alertness; minimal interference with activity	Some interference with activity	Unable to achieve normal level of alertness; prevents daily activity	N/A
Illness or clinical adverse event	Minimal or no interference with activity	Some interference with activity not requiring medical intervention	Prevents daily activity and requires medical intervention	N/A
Vital Signs	Grade 1	Grade 2	Grade 3	Grade 4
Fever (Axillary)	38.0 – 38.4°C ¹⁰ 0.4 – 101.1°F	38.5 - 40°C 101.2 - 104°F	>40°C >104°F	N/A
Tachycardia – beats per minute (infants)	181-200	201-220	>220	N/A
(adults)	101 – 115	116 – 130	>130	ER visit or hospitalization for arrhythmia
Bradycardia – beats per minute(infants)(adults)	96-105	91-95	<91	N/A
	50 – 54	45 – 49	<45	ER visit or hospitalization for arrhythmia
Tachypnea – breaths per minute (infants) (adults)	61-65	66-69	>69	N/A
(audits)	17 – 20	21 – 25	>25	Intubation

.....

Hypertension (systolic) – mm Hg (adults only)	141 – 150	151 – 155	>155	ER visit or hospitalization for malignant hypertension
Hypertension (diastolic) – mm Hg (adults only)	91 – 95	96 – 100	>100	ER visit or hospitalization for malignant hypertension
Hypotension (systolic) – mm Hg (adults only)	85 - 89	80 – 84	<80	ER visit or hospitalization for hypotensive shock
Respiratory Distress/ Hypoxia	Wheezing, nasal flaring or retractions; minimal or no interference with activity	Some interference with activity or pulse oximetry <95%	Prevents normal activity or pulse oximetry <90%	N/A
All other AEs	No interference with normal daily activity, minor severity. No treatment required.	Minimal interference with normal daily activity, moderate severity, treatment may be required	Significant interference with normal daily activity, treatment required	Severe incapacitation, urgent treatment or hospital admission required

APPENDIX C. TABLE OF TOXICITY REFERENCE RANGES FOR GRADING SAFETY LABORATORY EVENTS

Serum/Plasma Chemistry	Grade 1	Grade 2	Grade 3	Grade 4
Sodium – hyponatremia				
mEq/L or mmol/L:	132 – 134	130 – 131	<130	N/A
Sodium – hypernatremia		147-148		
mEq/L or mmol/L:	145- 146	147-140	>148	N/A
Potassium – hyperkalemia				
mEq/L or mmol/L				N/A
≤ 1 year:	5.3 – 5.4	5.5 – 5.6	>5.6	14// (
1 - 2years:	5.1 – 5.2	5.3 – 5.4	>5.4	
Potassium – hypokalemia	0.5.00	0000	0.4.00	N/A
mEq/L or mmol/L:	3.5 – 3.6	3.3 – 3.4	3.1 – 3.2	
Glucose – hypoglycemia	55.50	50.54	.50	N1/A
mg/dL:	55-59	50-54	<50	N/A
mmol/L:	3.0 – 3.2	2.8 – 2.9	<2.8	
Glucose – hyperglycemia	404 440	444 405	. 405	
Fasting - mg/dL:	101 – 110	111 – 125	>125	NI/A
mmol/L:	5.7 – 6.0	6.1 – 6.8	>6.8	N/A
Random – mg/dL:	110 - 125 6.1 – 6.8	126 - 200	>200	
mmol/L:	0.1 - 0.0	6.9 – 11.0	>11.0	
Blood urea nitrogen (BUN) –				
increased	21 – 24	25 – 28	>28	N/A
mg/dL: mmol/L:	7.5 – 8.9	9.0 – 10.0	>10.0	
Creatinine – increased				
mg/dL:	0.8 – 0.9	1.0 – 1.2	>1.2	N/A
umol/L:	66 - 82	83 – 100	>100	19/7
Calcium – hypocalcemia	00 - 02	00 100	7 100	
mg/dL:	8.0 – 8.4	7.5 – 7.9	<7.5	N/A
mmol/L:	2.00 – 2.10	1.87 – 1.99	<1.87	14// (
Calcium – hypercalcemia				
mg/dL:	11.1-11.3	11.4 – 11.6	>11.6	N/A
mmol/L:	2.78 – 2.84	2.85 – 2.92	>2.92	
Magnesium – hypomagnesemia				
mg/dL:	1.3 – 1.5	1.1 – 1.2	<1.1	N/A
mmol/L:	0.52 - 0.62	0.43 - 0.51	<0.43	
Phosphorus – hypophosphatemia				
mg/dL:	2.3 - 2.5	2.0 - 2.2	<2.0	N/A
mmol/L:	0.73 – 0.80	0.63 - 0.72	<0.63	
Albumin – hypoalbuminemia				
g/dL:	2.5 – 2.7	2.2 - 2.4	<2.2	N/A
g/L:	25 – 27	22 – 24	<22	
Total protein – hypoproteinemia				
g/dL:	4.4 - 4.6	4.1 - 4.3	<4.1	N/A
g/L:	44 – 46	41 – 43	<41	
Alkaline phosphatase (ALP)	1.1 – 2.0 x	2.1 – 3.0 x ULN	3.1 – 10 x ULN	>10 x ULN
- increased	ULN**			
Liver Function Tests (LFT) AST, ALT, GGT – increased	1.1 – 2.5 x ULN	2.6 – 5.0 x ULN	5.1 – 10 x ULN	>10 x ULN
Bilirubin (with any increase in LFT) - increased	1.1 – 1.25 x ULN	1.26 – 1.5 x ULN	1.51 – 1.75 x ULN	>1.75 x ULN
- 1110164364	l OLIN	l OLIN	OLIN	

Serum/Plasma Chemistry	Grade 1	Grade 2	Grade 3	Grade 4
Bilirubin (with normal LFT) - increased	1.1 – 1.5 x ULN	1.6 – 2.0 x ULN	2.1 – 3.0 – x ULN	>3.0 x ULN
Cholesterol – increased mg/dL: mmol/L:	171 - 185 5.1 – 5.5	186 – 199 5.6 – 6.0	>199 >6.0	N/A
Pancreatic enzymes amylase, lipase – increased	1.1 – 1.5 x ULN	1.6 – 2.0 x ULN	2.1 – 5.0 x ULN	>5.0 x ULN

Hematology	Grade 1	Grade 2	Grade 3	Grade 4
Hemoglobin g/dL				
≤ 21 days	12.0 – 13.0	10.0 – 11.9	9.0 - 9.9	<9.0
22 – 35 days	9.5 – 10.5	8.0 - 9.4	7.0 - 7.9	<7.0
36 days – 56 days	8.5 – 9.4	7.0 - 8.4	6.0 - 6.9	<6.0
≥ 57 days ≤ 6 months	9.0 – 9.4	8.5 – 8.9 9.5 – 9.9	<8.5 <9.5	N/A
6 mo - 2yr	10.0 – 10.4	9.5 – 9.9	<9.5	N/A
WBC – increased cells/mm³	18,700 – 22,000	22,100 – 25,000	>25,000	N/A
WBC – decreased cells/mm ³	4,500 – 5,500	3,500 – 4,400	<3,500	N/A
Lymphocytes - decreased cells/mm ³	2,000-2,700	1,500-1,900	<1,500	N/A
Neutrophils - decreased				
Age (> 7 days – 3 mo)				
cells/mm ³ :	1,000 - 1,300	750 – 999	< 750	N/A
(≥ 3 mo)				
cells/mm ³ :	750-990	500-740	<500	N/A
Eosinophils – increased cells/mm ³	850 – 1,500	1,501 – 5,000	>5,000	N/A
Platelets - decreased cells/mm ³	125,000 – 140,000	100,000 – 124,000	<100,000	N/A
Prothrombin Time (PT)/International normalized ratio (INR) – increased	1.1 – 1.2 x ULN**	1.3 – 1.4 x ULN	>1.4 x ULN	N/A
Partial thromboplastin time (PTT) – increased	1.1 – 1.2 x ULN	1.3 – 1.4 x ULN	>1.4 x ULN	N/A
Fibrinogen – increased				
mg/dL:	400 – 500	501 – 600	>600	N/A
g/L:	4.00 - 5.00	5.01 – 6.00	>6.00	
Fibrinogen – decreased				
mg/dL:	150 - 170	125 – 149	<125	N/A
g/L:	1.50 – 1.70	1.25 – 1.49	<1.25	

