6 STUDY ENROLLMENT AND WITHDRAWAL

6.1 Participant Inclusion Criteria

Participants must meet all of the following criteria at the time of randomization:

- 1. Male or female neonates within 96 hours of birth.
- 2. Written informed maternal consent, including permission to access maternal antenatal, postnatal and infant medical records.
- 3. Infant participants and their caregivers available for study follow-up and display the willingness and capacity to comply with study procedures.
- 4. Neonates must be in good general health during pregnancy and delivery, as assessed by medical history and focused physical examination.
- 5. Birth weight ≥ 2450 grams.
- 6. Appar score at 5 minutes \geq 7.
- 7. A maternal HIV test result (rapid test, ELISA or PCR) taken within 30 days of delivery must be available, documented and negative.
- 8. Estimated gestational age ≥ 37 weeks.
- Mother has not participated in a clinical trial within 3 months prior to the infant's birth, and
 if breast-feeding, mother should not participate in a clinical trial during the 12 months of
 study follow up.
- 10. Mother has never participated in a TB vaccine trial before.
- 11. Infant may not participate in any other clinical trial from birth, and for the 12 months of follow up.

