8.2 Enrollment/Baseline

Study Day 0 (within 96 hours of birth)

Pre-vaccination:

- 1. Verbally reconfirm maternal consent.
- Confirm absence of acute illness in infant.
- 3. Medical history and update of concomitant medication.
- 4. Screening for potential new TB exposure and TB symptoms.
- 5. Vital signs:

- Heart rate, respiratory rate, weight, recumbent length.
- Axillary temperature: must be <38°C.
- 6. History and physical examination by investigator.
- 7. Confirm eligibility for study entry and vaccination.
- 8. Complete Vaccine Request Form, send to study vaccine manager (study pharmacist) who will randomise participant into a study arm according to the next available treatment number in the final randomisation schedule, and then prepare study vaccine.

Vaccination (by Vaccination Nurse):

- 1. Inspect syringe and vaccine volume, confirm PID number, date and time of dose preparation.
- 2. Administer study vaccine intradermally into left deltoid area of the infant's arm. Record date and time of vaccination, presence of a bleb. Apply Opsite plaster.

Post-vaccination:

- 1. Monitor participant for acute adverse events for at least 60 minutes after vaccination.
- 2. Obtain 60±10 minutes post-immunization vital signs (pulse, axillary temperature).
- 3. Examine site of injection 60±10 minutes post-immunization (includes measurement of redness, swelling, and ulceration); replace Opsite plaster.
- 4. Record any adverse events, including systemic solicited adverse events, unsolicited adverse events, solicited and unsolicited injection site reactions, and serious adverse events (including concomitant medications).
- 5. Distribute and review diary card and diary card instructions with participant; review injection site care instructions and distribute Opsite plasters and plastic Ziploc bags.

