8.3 Follow-up

Study Day 7

Allowable window for clinic visit is 7±3 days from Study Day 0 visit date.

- 1. Verbally reconfirm consent.
- 2. Update medical history including use of medications.
- 3. Screening for potential new TB exposure and TB symptoms.
- 4. Record feeding practice.
- 5. Vital signs (heart rate, respiratory rate, axillary temperature, weight and recumbent length).
- 6. Focused physical examination.
- 7. Collect and review solicited AE and medication diary card entries for completeness and accuracy. Redistribute AE and medication diary card.
- 8. Record any adverse events, including systemic solicited adverse events, unsolicited adverse events, solicited and unsolicited injection site reactions, and serious adverse events (including concomitant medications).
- 9. Examine site of injection (includes measurement of redness, swelling, and ulceration) and take a pus swab if discharge present.

10. Blood collection for:

- Serum chemistry: includes AST, ALT, GGT, total bilirubin, creatinine.
- Hematology: includes full blood count with differential, and platelet count.

Study Day 28

Allowable window for clinic visit is 28±3 days from Study Day 0 visit date.

- 1. Verbally reconfirm consent.
- 2. Update medical history including use of medications.
- 3. Screening for potential new TB exposure and TB symptoms.
- 4. Record feeding practice.
- 5. Vital signs (heart rate, respiratory rate, axillary temperature, weight and recumbent length).
- 6. Focused physical examination.
- 7. Collect and review solicited AE and medication diary card entries for completeness and accuracy.
- 8. Record any adverse events, including systemic solicited adverse events, unsolicited adverse events, solicited and unsolicited injection site reactions, and serious adverse events (including concomitant medications).
- 9. Examine site of injection (includes measurement of redness, swelling, and ulceration) and take a pus swab if discharge present.
- 10. Blood collection for:
 - Immunogenicity WB-ICS

Study Day 56

Allowable window for clinic visit is 56±7 days from Study Day 0 visit date.

- 1. Verbally reconfirm consent.
- 2. Update medical history including use of medications.
- 3. Screening for potential new TB exposure and TB symptoms.
- 4. Record feeding practice.
- 5. Vital signs (heart rate, respiratory rate, axillary temperature, weight and recumbent length).
- 6. Focused physical examination.

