When an adverse event is judged to be related to an investigational product, is judged to be serious and unexpected, and is in a participant who received active vaccine, it is a SUSAR (suspected unexpected serious adverse reaction) and is subject to expedited reporting.

10.2.4 Procedures to be Followed in the Event of Abnormal Laboratory Test Values or Abnormal Clinical Findings

Results from clinical assessments and laboratory tests obtained on the study must be reviewed by the investigator, and the participant managed in accordance with the clinical trial site policies. The clinical significance of any change in a vital sign or laboratory parameter will be determined by the investigator and may be reported as an adverse event at the discretion of the investigator (using the toxicity tables in Appendix B, C and D to grade severity). Additional laboratory tests may be performed if the investigator deems them to be necessary to fully evaluate an adverse event. In the event that the investigator elects to order non-protocol-specified laboratory tests, the investigator must record the rationale for the tests and a determination of clinical significance of the result in the source documents. The investigator must keep the medical monitor informed of vaccine-related adverse events of clinical significance.

Abnormal results and findings will be discussed as applicable with the participant, and the participant will be referred for follow-up with their healthcare provider if necessary.

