12.4.4.2 Clinical Laboratory and Vital Sign Parameters

For each clinical laboratory parameter and vital sign parameter pre-specified in the protocol, summary statistics for continuous parameters will be presented by treatment group for all pre-and post-vaccination assessments and for change from pre-vaccination to post-vaccination assessments.

The number and percentage of participants with post-vaccination Grade 3 or higher clinical laboratory values or vital sign values (Appendices B, C and D) will be tabulated at each post-vaccination time point and overall. Clinical laboratory and vital sign abnormalities will also be reported as adverse events as applicable and will be included in the summaries of adverse events

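### Appendix C has no neutrophil band for infants aged 7 days or younger, although the only scheduled blood count may be drawn at about 4 to 14 days of age; its creatinine limits also differ by unit

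*Combined protocol and SAP*

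**What the plan says.** **Age at vaccination.** Section 6.1 admits "Male or female neonates within 96 hours of birth", and section 8.2 places vaccination at "Study Day 0 (within 96 hours of birth").

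**Timing of the count.** For the Study Day 7 visit, section 8.3 states: "Allowable window for clinic visit is 7±3 days from Study Day 0 visit date". The blood list at that visit reads "Hematology: includes full blood count with differential, and platelet count", so neutrophils are measured. In Appendix A the row "Safety blood sampling (mL") has an entry at D7 only. Section 10.2.4 adds that "Additional laboratory tests may be performed if the investigator deems them to be necessary to fully evaluate an adverse event", so this is the single scheduled count, not necessarily the only one.

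**Grading.** The neutrophil row of Appendix C has two age bands. One is headed "Age (> 7 days – 3 mo") and the other starts at 3 months. In the younger band, Grade 3 is a count below 750 cells/mm3. In the same appendix, hemoglobin has a band for 21 days or younger, and Appendix D grades bilirubin from the first day of life.

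**Use of the grades.** Section 12.4.4.2 tabulates "The number and percentage of participants with post-vaccination Grade 3 or higher clinical laboratory values" at each post-vaccination time point and overall, taking the grades from Appendices B, C and D.

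**Creatinine**, also a Day 7 test, is graded in Appendix C in two units: 0.8 to 0.9, 1.0 to 1.2 and above 1.2 mg/dL for Grades 1 to 3; and 66 to 82, 83 to 100 and above 100 umol/L. No grading unit is named.

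**The concern.** The grading table does not cover the start of the age range in which the scheduled sample may be taken. Take a count of 600 cells/mm3: at 9 days of age it is Grade 3 under Appendix C, and at 6 days it has no grade there. The older neutrophil band, from 3 months, can never apply to the scheduled sample.

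Safety by MTBVAC dose against BCG is a primary objective, and each infant has one scheduled count. An ungradable infant left in the denominator is silently counted as not Grade 3; an infant left out makes the denominator smaller than the number bled. The plan does not say which applies, so two analysts could produce different tables from the same data. The creatinine row raises a smaller problem of the same kind: the grade can depend on the unit in which the result is reported.

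**Working it through.** The plan states no share of ungradable infants, so there is no figure of its own to reproduce.

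**Age at the scheduled draw.** Age at vaccination is 0 to 4 days (96 hours, sections 6.1 and 8.2). The visit is 7 − 3 = 4 to 7 + 3 = 10 days after vaccination (section 8.3). Age at draw is the sum: 0 + 4 = 4 to 4 + 10 = 14 days. Appendix C applies only above 7 days.

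**Share aged 7 days or younger.** This needs distributions that the documents do not give. Assumed cases:

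- *Exact ages, both windows evenly filled.* Age is uniform over 0 to 4 days and visit uniform over 4 to 10 days. The region with a sum of at most 7 is a triangle with sides 3 and 3: (3 × 3 / 2) / (4 × 6) = 4.5 / 24 = 18.75%, or about 19 of 99 infants.
- *Whole days, age 0 to 3, visits D4 to D10.* Qualifying pairs: 4 + 3 + 2 + 1 = 10 of 4 × 7 = 28, which is 35.7%, or about 35 of 99.
- *Whole days, age 0 to 4, visits D4 to D10.* 10 of 5 × 7 = 35, which is 28.6%, or about 28 of 99.
- *Every visit on D7.* On whole days, 1 of 4 = 25% for ages 0 to 3 and 0% for ages 1 to 4. On exact age, essentially 0%.
- *Vaccination on day 0 or 1, whole days, visits D4 to D10.* (4 + 3) / 14 = 50%.

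Per MTBVAC cohort of 25, the evenly spread cases give 0.1875 × 25 = 4.7 to 0.357 × 25 = 8.9 infants.

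**Effect on the table.** Let u be the ungradable share, and suppose the true Grade 3 proportion is the same in gradable and ungradable infants (an assumption). If ungradable infants stay in the denominator, the tabulated proportion is (1 − u) times the true one: 1 − 0.1875 = 0.81 or 1 − 0.357 = 0.64 times.

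**Creatinine.** The factors implied by the table's own cut-points are 66/0.8 = 82.5, 82/0.9 = 91.1, 83/1.0 = 83.0 and 100/1.2 = 83.3 umol/L per mg/dL. No single factor fits them at face value. With the conversion constant 88.4 (assumed, not in the documents), 1.2 × 88.4 = 106.1 umol/L and 100 / 88.4 = 1.13 mg/dL. Whole-number results from 101 to 106 umol/L are therefore Grade 3 in one unit and Grade 2 in the other. If mg/dL results are rounded to one decimal, the disagreement extends to 110 umol/L (110 / 88.4 = 1.24, reported as 1.2). At the lower cut-points, 66 and 83 umol/L also change grade, by rounding only.

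**The case against.** The strongest reply concerns size. Whole-day counting treats an infant aged 7 days and some hours as 7 days or younger. On exact age, an infant seen a full 7 days after vaccination is already past 7 days, so the gap arises essentially at visits on D4 to D6. Section 8.1 has the mother return to the clinic on a given date for Day 0, which makes vaccination on the day of birth less typical, and visits normally aim at D7. This stands: the share may be small. It does not remove the gap, because the protocol's own window permits those visits.

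Second, section 10.2.1 gives a general severity scale for events outside the toxicity tables, Appendix B has a row for all other events, and section 10.2.4 leaves clinical significance to the investigator. This also stands for reported adverse events. But those scales rest on interference with activity and need for treatment; they hold no neutrophil limit, and section 12.4.4.2 tabulates laboratory values.

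Third, the table is descriptive, no formal testing is planned (section 12.1), and randomisation within cohorts should make the share similar for MTBVAC and BCG in a cohort. That limits bias within a cohort. Doses are compared across cohorts enrolled in sequence, where the share could differ.

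On creatinine, the mismatch has no effect on consistency if one laboratory reports in one unit throughout. The documents do not say whether this is so.

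**Conclusion.** The gap is real: Appendix C has no neutrophil limit for an age at which the single scheduled count may be drawn. Affected infants have no Appendix C grade and cannot count as Grade 3 or higher in the section 12.4.4.2 table. The share is roughly 19% to 36% if ages and visits fill the windows evenly, near 0% if visits cluster on or after D7, and higher than 36% if vaccination and visits are early. All these figures rest on assumed distributions.

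A reader might infer more, and the documents do not support it:

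- That about a third of infants are affected, or that a third is an upper limit. It is one result among several and depends on counting whole days.
- That the Grade 3 neutropenia rate is understated by a known amount. The documents give neither a neutropenia rate nor the ungradable share.
- That these infants can have no severity at all, or that the pausing rules cannot operate. A reported event can be graded on the general scale. Rule 5 in section 10.5 depends on related events in two or more participants, and rule 6 covers any pattern of concern.

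The creatinine mismatch is a separate, narrow point, about 101 to 106 umol/L, and it matters only according to the reporting unit. The tables were machine-read, so a lost neutrophil row cannot be fully excluded, but both bands and their limits are intact and nothing suggests one.

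**What to change.** - Reconcile the neutrophil age bands in Appendix C with the Day 7 sampling window, so that every age from about 4 days is covered. The limits are for the sponsor's clinicians to set; none is proposed here.
- Until then, report Grade 3 or higher neutrophils with only gradable infants in the denominator, and state the number not gradable by arm and cohort. Say whether age is counted in exact time or completed days. The SAP, due before database lock (section 12.4), can hold this rule.
- Reconcile the two creatinine scales, or name the one unit used for grading.

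The cost is a table correction in Appendix C, a denominator rule in the SAP and, in the meantime, a smaller stated denominator for neutrophils. No new samples are needed.
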